### Endpoints Related to Skin Disease

- Proportions of participants who achieve  $\geq 75\%$ ,  $\geq 90\%$ , and 100% improvement in Psoriatic Area and Severity Index (PASI) score from baseline by visit over time through Week 156 among the participants with  $\geq 3\%$  body surface area (BSA) psoriatic involvement and an Investigator's Global Assessment (IGA) score of  $\geq 2$  (mild) at baseline.
- Proportion of participants with a psoriasis response of an IGA (ie, an IGA-psoriasis score of 0 [cleared] or 1 [minimal] AND  $\geq 2$ -grade reduction from baseline) by visit over time through Week 156 among the participants with  $\geq 3\%$  BSA psoriatic involvement and an IGA score of  $\geq 2$  (mild) at baseline.
- Proportion of participants with an IGA score of 0 (cleared) by visit over time through Week 156 among the participants with  $\geq 3\%$  BSA psoriatic involvement and an IGA score of  $\geq 2$  (mild) at baseline.
- Change and percent change from baseline in PASI score by visit over time through Week 156 among the participants with  $\geq 3\%$  BSA psoriatic involvement and an IGA score of  $\geq 2$  (mild) at baseline.
- Proportion of participants who achieve both PASI 75 and ACR 20 responses by visit over time through Week 156 among the participants with  $\geq 3\%$  BSA psoriatic involvement and an IGA score of  $\geq 2$  (mild) at baseline.

- Proportion of participants who achieve both PASI 75 and modified PsARC response by visit over time through Week 156 among the participants with  $\geq 3\%$  BSA psoriatic involvement and an IGA score of  $\geq 2$  (mild) at baseline.
- Proportion of participants who achieve a Dermatology Life Quality Index (DLQI) score of 0 or 1 by visit through Week 156 among the participants with baseline DLQI score  $> 1$  and with  $\geq 3\%$  BSA psoriatic involvement and an IGA score of  $\geq 2$  (mild) at baseline.
- Proportion of participants who achieve  $\geq 5$ -point improvement from baseline in DLQI score by visit through Week 156 among the participants with baseline DLQI score  $\geq 5$  and with  $\geq 3\%$  BSA psoriatic involvement and an IGA score of  $\geq 2$  (mild) at baseline.
- Change from baseline in DLQI score by visit through Week 156 among the participants with  $\geq 3\%$  BSA psoriatic involvement and an IGA score of  $\geq 2$  (mild) at baseline.

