5.3.6.3.3. DLQI Related Endpoints

CCI

The DLQI related Other Efficacy endpoints include:

- Change from baseline in DLQI score by visit through Week 156 among the participants with $\geq 3\%$ BSA psoriatic involvement and an IGA score of ≥ 2 (mild) at baseline.
- Proportion of participants who achieve a DLQI score of 0 or 1 by visit through Week 156 among the participants with baseline DLQI score >1 and with $\geq 3\%$ BSA psoriatic involvement and an IGA score of ≥ 2 (mild) at baseline.
- Proportion of participants who achieve ≥ 5 -point improvement from baseline in DLQI score by visit through Week 156 among the participants with baseline DLQI score ≥ 5 and with $\geq 3\%$ BSA psoriatic involvement and an IGA score of ≥ 2 (mild) at baseline.

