6	Proportion of participants with IGA response	mFAS with $\geq 3\%$ BSA and IGA ≥ 2 at baseline	NRI for MAR not due to Natural Disaster or Major Disruption	
 Summarized descriptively Response rates, and treatment difference in response rates and 95% CI and pvalue, based on GLMM
7	Proportions of participants with IGA score of 0	mFAS with $\geq 3\%$ BSA and IGA ≥ 2 at baseline	NRI for MAR not due to Natural Disaster or Major Disruption	
 Summarized descriptively Response rates, and treatment difference in response rates and 95% CI and pvalue, based on GLMM
8	Change from baseline in DLQI score	mFAS with $\geq 3\%$ BSA and IGA ≥ 2 at baseline	-	
 Summarized descriptively LS mean (95% CI) for each intervention group, LS mean difference (95% CI) and p-values for differences between groups based on MMRM
9	Proportions of participants with DLQI score of 0 or 1	mFAS with DLQI score ≥ 1, $\geq 3\%$ BSA and IGA ≥ 2 at baseline	NRI for MAR not due to Natural Disaster or Major Disruption	
 Summarized descriptively Response rates, and treatment difference in response rates and 95% CI and pvalue, based on GLMM.
10	Proportions of participants with ≥ 5 -point improvement in DLQI score	mFAS with DLQI score ≥ 5, $\geq 3\%$ BSA and IGA ≥ 2 at baseline	NRI for MAR not due to Natural Disaster or Major Disruption	
 Summarized descriptively Response rates, and treatment difference in response rates and 95% CI and pvalue, based on GLMM.

'-' indicates no missing data rules to be applied

ENDPOINTS BY VISIT AFTER WEEK 24 THROUGH WEEK 48 AT WEEK-48 DBL, USING ADJUSTED COMPOSITE ESTIMAND

1, 2, 8	Same as through Week 24	Same as through Week 24	Same as through Week 24	
 Summarized descriptively LSMeans and 95% CI by intervention group based on MMRM model
---------	-------------------------	-------------------------	-------------------------	--

Table 11: Summary of Estimands, Analysis Sets, Data Handling Rules, and Analysis Methods for Endpoints of Skin Disease

	Endpoint	Analysis Set	Missing Data Rules	Analysis Methods
3, 4, 5, 6, 7, 9, 10	Same as through Week 24	Same as through Week 24	Same as through Week 24	
 • Summarized descriptively • Response rates by intervention group based on GLMM

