5.3.6.4. Endpoints Related to Psoriasis of the Nails

In this study, Other Efficacy endpoints for psoriasis of the nails include those related to mNAPSI and PGA-F.

All Other Efficacy endpoints related to psoriasis of the nails will be conducted under the mFAS population among participants with presence of psoriatic nail disease as measured by the instrument in question for the Adjusted Composite Estimand, and mFAS-UKR population among participants with presence of psoriatic nail disease as measured by the instrument in question for the Treatment Policy Estimand, **unless** explicitly stated otherwise.

5.3.6.4.1. mNAPSI Related Endpoints

CCI

CCI

The mNAPSI related Other Efficacy endpoints include:

- Percent change from baseline in total fingernail mNAPSI score by visit over time through Week 156 among the participants with total fingernail mNAPSI score >0 at baseline.
- Proportions of participants who achieve total fingernail mNAPSI 50/75/100 response by visit over time through Week 156 among the participants with total fingernail mNAPSI score >0 at baseline.

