5.3.6.4.3. Method of Analysis

In general, the same methods of analysis for the Other Efficacy endpoints related to reduction of signs and symptoms and physical function in Section 5.3.6.2.10 will also be used for those related to nail psoriasis.

Table 12 summarizes the analyses for supportive efficacy endpoints related to nail psoriasis, the methods for analyses, and the data handling rules used.

Table 12: Summary of Estimands, Analysis Sets, Data Handling Rules, and Analysis Methods for Endpoints of Nail Psoriasis

	Endpoint	Analysis Set	Missing Data Rules	Analysis Methods
ENDPOINTS BY VISIT THROUGH WEEK 24 AT WEEK-24 DBL, ADJUSTED COMPOSITE ESTIMAND				
1	Percent change from baseline in total fingernail mNAPSI score	mFAS with total fingernail mNAPSI score \geq 0 at baseline	-	
 Summarized descriptively LS mean (95% CI) for each intervention group, LS mean difference (95% CI) and p-values for differences between groups based on MMRM -
2	Proportions of participants with total fingernail mNAPSI 50/75/100 response	mFAS with total fingernail mNAPSI score \geq 0 at baseline	NRI for MAR not due to Natural Disaster or Major Disruption	
 Summarized descriptively Response rates, and treatment difference in response rates and 95% CI and pvalue, based on GLMM
3	Proportion of participants with PGA-F response	mFAS with PGA-F score \geq 2	NRI for MAR not due to Natural Disaster or Major Disruption	
 Summarized descriptively Response rates, and treatment difference in response rates and 95% CI and pvalue, based on GLMM

'-' indicates no missing data rules to be applied

ENDPOINTS BY VISIT AFTER WEEK 24 THROUGH WEEK 48 AT WEEK-48 DBL, USING ADJUSTED COMPOSITE ESTIMAND

1	Same as through Week 24	Same as through Week 24	Same as through Week 24	
 Summarized descriptively LSMeans and 95% CI by intervention group based on MMRM model
2, 3	Same as through Week 24	Same as through Week 24	Same as through Week 24	
 Summarized descriptively Response rates by intervention group based on GLMM

ENDPOINTS BY VISIT AFTER WEEK 48 THROUGH WEEK 96 AT WEEK-96 DBL, AND AFTER WEEK 96 THROUGH WEEK 156 AT FINAL DBL, USING ADJUSTED COMPOSITE ESTIMAND

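### The baseline cut-offs in SAP Table 11 row 9 (DLQI at least 1) and Table 12 rows 1-2 (mNAPSI at least 0) contradict the endpoint definitions, which require above 1 and above 0

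*SAP*

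**What the plan says.** **DLQI 0/1.** SAP 5.3.6.3.3 limits this endpoint to a subset: "among the participants with baseline DLQI score >1", together with the body-surface and IGA conditions that apply to all skin endpoints. The protocol has the same baseline limit for "Proportion of participants who achieve a Dermatology Life Quality Index (DLQI) score of 0 or 1 by visit through Week 156", both in the Synopsis and in Section 3. In SAP Table 11 (Section 5.3.6.3.4), row 9 is headed "Proportions of participants with DLQI score of 0 or 1". Its analysis-set cell begins "mFAS with DLQI score" and continues with a greater-than-or-equal sign and 1.

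**mNAPSI.** SAP 5.3.6.4.1 limits both the percent-change endpoint and the 50/75/100 response endpoint in the same way: "among the participants with total fingernail mNAPSI score >0 at baseline". The protocol agrees in both places. In SAP Table 12 (Section 5.3.6.4.3), row 1 is "Percent change from baseline in total fingernail mNAPSI score" and row 2 is the 50/75/100 response. The analysis-set cell for each begins "mFAS with total fingernail mNAPSI score" and continues with a greater-than-or-equal sign and 0.

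**Reach.** In both tables the rows for the later periods carry the Week 24 analysis sets forward, and the Treatment Policy analyses repeat the same endpoints on mFAS-UKR.

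**Status.** SAP 5.3.6 places all of these among the Other Efficacy endpoints, outside the multiplicity procedure, with nominal p-values.

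**The concern.** The strict inequality has a purpose in each definition. For DLQI it removes anyone who is at the target before treatment starts. For mNAPSI it removes anyone without fingernail disease on that instrument. Such people can be enrolled, because inclusion criterion 7 accepts a qualifying plaque and/or nail changes.

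The cells as they read undo both protections. SAP 5.3.6.3 and 5.3.6.4 also set their general populations subject to any explicit statement to the contrary. A programmer working from a column headed as the analysis set could take the cell as that statement. The result would be a DLQI denominator containing responders at entry, and an mNAPSI percent change that cannot be calculated for part of its own set.

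**Working it through.** The plan gives no figure to reproduce here, so the check is of boundary values.

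**Step 1: which baseline values differ between cell and definition.**

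| Baseline value | In the table's set | In the defined set | Consequence if included |
|---|---|---|---|
| DLQI 0 | no | no | none |
| DLQI 1 | yes | no | already at 0/1 |
| DLQI 2 or more | yes | yes | none |
| mNAPSI 0 | yes | no | percent change divides by 0 |
| mNAPSI above 0 | yes | yes | none |

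The DLQI discrepancy therefore concerns participants at exactly 1. The mNAPSI discrepancy concerns participants at exactly 0. For a score that cannot be negative, a condition of at least 0 excludes nobody.

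**Step 2: are the neighbouring cut-offs sound?** Yes. Table 11 row 10 (DLQI at least 5) and Table 12 row 3 (PGA-F at least 2) match their definitions. The mismatch is confined to three cells.

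**Step 3: size for DLQI 0/1.** None of the following inputs is in the documents; all are assumptions.
- f is the share of the at-least-1 set with baseline exactly 1: 2%, 5% or 10%.
- s is the response rate of those participants, equal in the arms compared: 60% to 90%.
- The true response among participants with baseline above 1 is 15% on placebo and 45% on guselkumab, a difference of 30 points.

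The observed crude rate in an arm with true rate p is (1 - f) × p + f × s. The second term is the same in both arms and cancels, so the observed difference is (1 - f) × 30.

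| f | Placebo, s = 60% to 90% | Guselkumab, s = 60% to 90% | Difference |
|---|---|---|---|
| 2% | 15.9% to 16.5% | 45.3% to 45.9% | 0.98 × 30 = 29.4 |
| 5% | 17.25% to 18.75% | 45.75% to 47.25% | 0.95 × 30 = 28.5 |
| 10% | 19.5% to 22.5% | 46.5% to 49.5% | 0.90 × 30 = 27.0 |

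For example, at f = 5% and s = 90%, placebo is 0.95 × 15 + 0.05 × 90 = 18.75 and guselkumab is 0.95 × 45 + 0.05 × 90 = 47.25. The difference is 28.5. The planned analysis is a GLMM, so this crude arithmetic is a guide to size only.

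**Step 4: mNAPSI.** Percent change is 100 × (value - baseline) / baseline, which is undefined at baseline 0. The effect on the 50/75/100 response depends on how a baseline of 0 is coded:
- Counted as full clearance, it raises the response rate.
- Treated as missing for an ordinary reason, it becomes non-response under the Adjusted Composite rules in SAP 5.3.6.2.10, which lowers the rate.
- Dropped as not calculable, it has no effect.

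The detailed mNAPSI text is redacted in both documents, so the coding cannot be settled and no size is put on it.

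**The case against.** **The signs may be misread.** All the disputed signs sit in table cells, and every prose statement of the same limits is right. The SAP text used here was extracted from a PDF and shows character errors elsewhere: LTE appears with a 7 in Appendix 14, JSN appears with an extra letter in Tables 14 and 17, and a less-than sign seems to be missing from the age categories in Table 16. An underlined greater-than sign would come out as greater-than-or-equal. This objection stands and makes the finding conditional. The agreement of the two tables does not answer it, since a systematic misreading would produce the same pattern.

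**The tables only summarise.** They are titled as summaries, and the definitions are in the endpoint sections and the protocol. This also stands. A reader might infer that the SAP has redefined these populations. The documents do not support that: the mNAPSI definitions just ahead of Table 12 say above 0, and the general rule in 5.3.6.4 requires nail disease on the instrument concerned. The intent is clear; what remains is a conflict that no other text corrects.

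**A participant with mNAPSI 0 trivially meets mNAPSI 100, so response is inflated in every arm.** This is a tempting reading, but the scoring rule is redacted, and a value treated as missing would count as non-response instead. Inflation is not shown for mNAPSI.

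**The DLQI shares are invented.** They are assumptions. The skin set already requires at least 3% body surface and an IGA of at least 2, so few participants may sit at exactly 1.

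**Conclusion.** As the text reads, three cells contradict the SAP's own endpoint definitions and the protocol. Following them would put participants already at target into the DLQI 0/1 analysis, and participants with no calculable percent change into the mNAPSI analysis.

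The consequence is small. The DLQI difference is diluted by about the share at baseline 1, provided those participants respond alike in all arms: 1.5 to 3 points out of 30 at an assumed share of 5% to 10%. For mNAPSI, the zero denominator is certain at baseline 0, but the effect on the response rates is not determinable.

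A reader might infer damage to the trial's main conclusions. There is none: ACR 20 and the modified vdH-S score, the power calculations and the type I error control are all untouched. This is a minor correction, conditional on the original PDF showing the same signs.

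**What to change.** First look at the three cells in the original PDF. If they do show greater-than-or-equal signs, set Table 11 row 9 to baseline DLQI above 1, and Table 12 rows 1 and 2 to baseline total fingernail mNAPSI above 0. The later-period rows and the mFAS-UKR analyses refer back to these cells and inherit the correction, so nothing else needs editing.

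The cost is one symbol in each of three cells. It restores the limits already stated in the protocol and needs no new data or decision. If the analysis programs already exist, confirm that they apply the strict inequalities.

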5.3.6.4. Endpoints Related to Psoriasis of the Nails

In this study, Other Efficacy endpoints for psoriasis of the nails include those related to mNAPSI and PGA-F.

All Other Efficacy endpoints related to psoriasis of the nails will be conducted under the mFAS population among participants with presence of psoriatic nail disease as measured by the instrument in question for the Adjusted Composite Estimand, and mFAS-UKR population among participants with presence of psoriatic nail disease as measured by the instrument in question for the Treatment Policy Estimand, **unless** explicitly stated otherwise.

5.3.6.4.1. mNAPSI Related Endpoints

CCI

CCI

The mNAPSI related Other Efficacy endpoints include:

- Percent change from baseline in total fingernail mNAPSI score by visit over time through Week 156 among the participants with total fingernail mNAPSI score >0 at baseline.
- Proportions of participants who achieve total fingernail mNAPSI 50/75/100 response by visit over time through Week 156 among the participants with total fingernail mNAPSI score >0 at baseline.

5.3.6.4.2. PGA-F Related Endpoints

CCI

The PGA-F related Other Efficacy endpoints include:

- Proportion of participants with PGA-F response by visit over time through Week 156 among the participants with PGA-F score ≥ 2 (mild) at baseline.

5.3.6.4.3. Method of Analysis

In general, the same methods of analysis for the Other Efficacy endpoints related to reduction of signs and symptoms and physical function in Section 5.3.6.2.10 will also be used for those related to nail psoriasis.

Table 12 summarizes the analyses for supportive efficacy endpoints related to nail psoriasis, the methods for analyses, and the data handling rules used.

Table 12: Summary of Estimands, Analysis Sets, Data Handling Rules, and Analysis Methods for Endpoints of Nail Psoriasis

	Endpoint	Analysis Set	Missing Data Rules	Analysis Methods
ENDPOINTS BY VISIT THROUGH WEEK 24 AT WEEK-24 DBL, ADJUSTED COMPOSITE ESTIMAND				
1	Percent change from baseline in total fingernail mNAPSI score	mFAS with total fingernail mNAPSI score \geq 0 at baseline	-	
 Summarized descriptively LS mean (95% CI) for each intervention group, LS mean difference (95% CI) and p-values for differences between groups based on MMRM -
2	Proportions of participants with total fingernail mNAPSI 50/75/100 response	mFAS with total fingernail mNAPSI score \geq 0 at baseline	NRI for MAR not due to Natural Disaster or Major Disruption	
 Summarized descriptively Response rates, and treatment difference in response rates and 95% CI and pvalue, based on GLMM
3	Proportion of participants with PGA-F response	mFAS with PGA-F score \geq 2	NRI for MAR not due to Natural Disaster or Major Disruption	
 Summarized descriptively Response rates, and treatment difference in response rates and 95% CI and pvalue, based on GLMM

'-' indicates no missing data rules to be applied

ENDPOINTS BY VISIT AFTER WEEK 24 THROUGH WEEK 48 AT WEEK-48 DBL, USING ADJUSTED COMPOSITE ESTIMAND

1	Same as through Week 24	Same as through Week 24	Same as through Week 24	
 Summarized descriptively LSMeans and 95% CI by intervention group based on MMRM model
2, 3	Same as through Week 24	Same as through Week 24	Same as through Week 24	
 Summarized descriptively Response rates by intervention group based on GLMM

ENDPOINTS BY VISIT AFTER WEEK 48 THROUGH WEEK 96 AT WEEK-96 DBL, AND AFTER WEEK 96 THROUGH WEEK 156 AT FINAL DBL, USING ADJUSTED COMPOSITE ESTIMAND

1	Same as through Week 24	Same as through Week 24	Same as through Week 24	
 Summarized descriptively LSMeans and 95% CI by intervention group based on MMRM model
2, 3	Same as through Week 24	Same as through Week 24	NRI for MAR not either: due to Natural Disaster or Major Disruption, OR not enter LTE due reason other than Lack of	
 Summarized descriptively Response rates by intervention group based on GLMM

Table 12: Summary of Estimands, Analysis Sets, Data Handling Rules, and Analysis Methods for Endpoints of Nail Psoriasis

	Endpoint	Analysis Set	Missing Data Rules	Analysis Methods
			Efficacy/Worsening PsA	

**ENDPOINTS BY VISIT THROUGH WEEK 24 AT WEEK-24 DBL,
AFTER WEEK 24 THROUGH WEEK 48 AT WEEK-48 DBL,
AFTER WEEK 48 THROUGH WEEK 96 AT WEEK-96 DBL, AND
AFTER WEEK 96 THROUGH WEEK 156 AT FINAL DBL, USING TREATMENT POLICY ESTIMAND
AND THE mFAS-UKR ANALYSIS SET INSTEAD OF THE mFAS**

- The endpoints analyzed using the Adjusted Composite Estimand for corresponding visits/DBL are repeated here, except:
No imputation will be applied and all analyses will be based on observed data
Continuous endpoints will use ANCOVA instead of MMRM; binary response endpoints will use CMH test with CI based on Wald statistics instead of GLMM for visits up to and including Week 24

5.3.6.5. Endpoints Related to HRQOL

In this study, Other Efficacy endpoints for health related quality of life (HRQOL) measures include questionnaires of FACIT-Fatigue and PsAID-12.

All Other Efficacy endpoints related to HRQOL will be conducted under the mFAS population for the Adjusted Composite Estimand, and mFAS-UKR population of the Treatment Policy Estimand, ***unless*** explicitly stated otherwise.

5.3.6.5.1. FACIT-Fatigue Related Endpoints

CCI

For more information, contact the Office of the Vice President for Research and Economic Development at [contact] or [contact].

For more information, contact the Office of the Vice President for Research and Economic Development at [contact] or [contact].

For more information, contact the Office of the Vice President for Research and the Office of the Vice President for Student Affairs.

© 2013 Pearson Education, Inc.

© 2013 Pearson Education, Inc.

© 2013 Pearson Education, Inc.

For more information, contact the Office of the Vice President for Research and Economic Development at [contact] or [contact].

For more information, contact the Office of the Vice President for Research and Economic Development at [contact] or [contact].

For more information, contact the Office of the Vice President for Research and Economic Development at [contact] or [contact].

For more information, contact the Office of the Vice President for Research and Economic Development at [contact] or [contact].

For more information, contact the Office of the Vice President for Research and Economic Development at [contact] or [contact].

For more information, contact the Office of the Vice President for Research and Economic Development at [contact] or [contact].

© 2013 Pearson Education, Inc. All Rights Reserved. May not be copied, scanned, or duplicated, in whole or in part. Due to electronic rights, some third party content may be suppressed from the eBook and/or eChapter(s). Editorial review has determined that any suppressed content does not materially affect the overall learning experience. Pearson Education, Inc. reserves the right to remove additional content at any time if subsequent rights restrictions require it.

The FACIT-Fatigue related Other Efficacy endpoint

CONFIDENTIAL – FOIA or c

- Change from baseline in FACIT-F by visit over time through Week 156.
- Proportion of participants who achieve ≥ 4 -point improvement from baseline in FACIT-F score by visit over time through Week 156.

5.3.6.5.2. PsAID-12 Related Endpoints

CCI

The PsAID-12 related Other Efficacy endpoints include:

- Change from baseline in PsAID-12 by visit over time through Week 156.

